Transcranial magnetic stimulation (TMS): Motor evoked potentials (MEPs) in the tibialis anterior and rectus femoris muscles will be evoked by TMS of the contralateral motor cortical leg area using a Magstim 200² stimulator (Magstim, UK) through a double cone coil and a monophasic current waveform delivered at 4-s intervals. The motor threshold for both muscles will be identified⁶⁵ and that intensity will be used to elicit and average twenty MEPs at each timepoint²⁴. Average MEP response amplitude will be used to quantify changes in corticospinal tract excitability¹⁵. If no motor threshold is detected at 100% device stimulation intensity due to SCI (and interrupted circuits), the 100% stimulation intensity or the maximum tolerable intensity will be used. MEP responses will be measured during rest and during an active contraction (Motor Tasks, see below) before and after BoMI training, as well as with and without SCS. To estimate changes in MEPs, response amplitudes under different conditions will be normalized to the baseline (before training, resting) response.

Motor tasks: Immediately before after the BoMI session, participants will wear a VR headset (Oculus Quest 2, Facebook, CA) to block their view. The IMUs on the legs will measure and digitize their leg joint angles. A real-time virtual representation of one of their joint angles will be presented through the VR. Participants will be asked to perform two tasks requiring different types of motor control. In the range-of-motion task, participants will be instructed to flex or extend their legs to surpass a virtual target of a specified amplitude. In the precision-control task, participants will have to move their joint and hold the position within a target range of a specified amplitude for 1 second. We will examine motor-evoked potentials elicited by TMS (*Aim 1*) and the StartReact response (*Aim 2*) as individuals perform the task under two conditions: with SCS and without SCS using the knee and ankle joints. As an alternative to the VR headset, a wall projector will be used to perform the motor tasks.

BoMI Training: Participants will perform visuo-spatial motor tasks over a 45min session with SCS. The tasks will consist of different types of game-like activities like center-out reaching, pong, solitaire, Tetris, and other flash games.

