Expected outcomes, potential problems, and alternative strategies: Based on previous studies by other groups, it is our expectation that MEP responses will be enhanced for the precision-control task in distal muscles (tibialis anterior), which are thought to require a high involvement from the corticospinal tract. *We hypothesize that SCS will further enhance the MEP response for these movements, but not for range-of-motion movements, or movements with proximal muscles (rectus femoris).*

The main challenge in this study will be the recruitment of a sufficiently large group of volunteers with spinal cord injuries in the C4-T9 level. If this will not be feasible, we will extend the study to individuals with lesions at the C2-C3 level that have complete or partial paralysis in the legs. Furthermore, we can seek to further extend the study to other hospitals in the St. Louis region like the Barnes Jewish Hospital, the Rehabilitation Institute of St. Louis, SSM Rehabilitation Hospital, and the VA Medical Center Spinal Cord Injury Program. Another potential difficulty may arise because of the high expected attrition with severely disabled volunteers. As a consequence, some evaluations might be interrupted. To preserve uniformity of statistical power across the study, we will retain the results of participants with an incomplete number of sessions in separate data sets. The analysis of incomplete data sets will take explicitly into account the causes for abandoning the study (e.g. dissatisfaction with the methodology, change in medical condition, etc).

Our approach will have –by design an objective—a degree of customization based on each individual’s specific mobility and potential for movement restoration with SCS. Therefore, there might be a small initial difference in performance. However, our previous studies have demonstrated an improvement in performance with training independent of differences in the BoMI map between subjects^{22,62,66,67}.

One possibility is that 45 minutes of BoMI training is not sufficient to observe changes in corticospinal and reticulospinal tract excitability within a single session. If this is the case, we will increase the duration of BoMI training to 2 hours. Twenty minutes to 2 hours of SCS and motor training have been shown to be sufficient to observe changes in motor function^{61,68,69} as well as spinal¹⁵, cortical²⁴, and subcortical¹¹ excitability in human subjects.

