Average MEP and StartReact responses (of 20 responses) will be used to quantify changes in corticospinal and reticulospinal tract excitability¹⁵. A paired sample t-test of response amplitude and latency (time from stimulation to muscle response) will be used to test the hypothesis that BoMI training with SCS results in enhanced corticospinal tract excitability during precision-control movements and reticulospinal tract excitability during range-of-motion movements. In addition, a Student's *t*-test with a Holm-Sidak adjustment for multiple comparisons will be performed to compare the difference between changes in corticospinal excitability induced by the type of motor task (precision control vs. range-of-motion), joint (ankle vs. hip), and group (control vs. SCI).

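### The MEP 'change' compared between tasks, joints and groups is not defined; if it is the ratio to the resting baseline, the comparison mixes rest-to-active facilitation with the training or SCS effect

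*Combined protocol and SAP*

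**What the plan says.** The Aim 1 part of Section 7.1 (the second section to carry that number), in its TMS paragraph, sets out the conditions: "MEP responses will be measured during rest and during an active contraction (Motor Tasks, see below) before and after BoMI training", and also with and without SCS. It then gives the rule for a change: "To estimate changes in MEPs, response amplitudes under different conditions will be normalized to the baseline (before training, resting) response".

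Section 8 describes two analyses of these responses. The first is a paired t-test "used to test the hypothesis that BoMI training with SCS results in enhanced corticospinal tract excitability during precision-control movements", with a parallel statement for the reticulospinal tract. The two members of the pair are not named, although the hypothesis implies after versus before training. The second is a Student's t-test "with a Holm-Sidak adjustment for multiple comparisons", intended to "compare the difference between changes in corticospinal excitability induced by the type of motor task", by joint and by group. Section 8 does not say what a change is.

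The expected-outcomes paragraph of Aim 1 adds: "it is our expectation that MEP responses will be enhanced for the precision-control task in distal muscles (tibialis anterior". It then hypothesizes that SCS will enhance these responses further. So the protocol expects a task and muscle difference in MEP size that exists before any SCS effect is added.

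**The concern.** The numerators include active contraction after training; the denominator is rest before training. For a post-training task MEP the normalized value is therefore the rest-to-active increase multiplied by the training effect. Compared across joints, tasks or groups, the first factor does not cancel. Tibialis anterior and rectus femoris have different resting denominators. Two tasks in one muscle share a denominator, but the numerator still carries any difference in facilitation between the tasks.

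Aim 1 asks which kinds of SCS-facilitated movement are mediated by the corticospinal tract. A significant joint or task contrast on the unsubtracted ratio could be read as an answer when it shows only that one muscle or task produces larger MEPs during contraction. And because the variable is left open, it could be chosen after the data are seen.

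**Working it through.** **Plan's own figure.** There is none to reproduce: the documents give no effect size, SD, alpha, sidedness or power for the MEP comparisons.

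**Inputs from the documents.** About 16 unimpaired participants per visit type (Section 7.2, Initial evaluation); 12 SCI participants (Section 8.4); Holm-Sidak adjustment over task, joint and group (Section 8).

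**Assumed inputs.** Two-sided 0.05. Log SD of participants' active/rest facilitation 0.4. Log SD of each block mean 0.25. Geometric-mean facilitation 3.0 in one cell and 3.0, 3.75, 4.5 or 6.0 in the other, so the ratio between cells is 1.0, 3.75/3 = 1.25, 4.5/3 = 1.5 or 6/3 = 2.0.

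**Step 1: what the ratio contains.** Let F = active-pre / rest-pre and T = active-post / active-pre. Then

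active-post / rest-pre = F × T.

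With no training effect (T = 1), the ankle-minus-hip contrast of this ratio is F(ankle) − F(hip), which is zero only if facilitation is equal. The contrast of log(active-post / active-pre) is log T(ankle) − log T(hip) = 0 whatever F is.

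**Step 2: error rates with no training and no SCS effect.** Within-person t-test on active-post / rest-pre, by simulation. The first Holm-Sidak step for three comparisons is 1 − 0.95^(1/3) = 0.01695.

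| Facilitation ratio | n=12, 0.05 | n=12, first step | n=16, 0.05 | n=16, first step |
|---|---|---|---|---|
| 1.25 | 14% | 5% | 17% | 8% |
| 1.5 | 36% | 18% | 47% | 27% |
| 2.0 | 76% | 53% | 89% | 73% |

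At a ratio of 1.0 there is no excess. The log after/before ratio stays at about 5% throughout at 0.05.

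**Step 3: sensitivity to the SDs.** With log SD of facilitation 0.5 and of block means 0.3, the n=16 rates at 0.05 are 12%, 31% and 70% for ratios 1.25, 1.5 and 2.0. At ratio 2.0 the rate is 91% if the facilitation SD is 0.3 and 38% if it is 0.8. With SDs 0.5 and 0.3, a group comparison of 16 versus 12 gives 10%, 27% and 63% if facilitation differs between groups by 1.25, 1.5 or 2.0.

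**Step 4: the charitable reading.** Suppose normalization is only scaling and the variable is (post − pre) / rest. With no true effect, the within-person rate is about 4% to 5% at every facilitation ratio. Now give both cells the same proportional gain, with facilitation 3 and 6:

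- 20% gain: 3 × 0.20 = 0.6 versus 6 × 0.20 = 1.2 resting units; log ratio ln 1.2 in both.
- 50% gain: 3 × 0.50 = 1.5 versus 6 × 0.50 = 3.0 resting units; log ratio ln 1.5 in both.

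At n=16 with the Step 2 SDs, the test of unequal change rejects in 11% (20% gain) and 31% (50% gain) of trials, against 5% for the log ratio.

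**The case against.** The strongest reply is that nothing here is contradictory. A reader might infer that Section 8 defines change as after versus before training and so conflicts with Section 7.1. It does not: it writes no definition, and its first test only implies one. Within a muscle, post/rest and pre/rest share a denominator, so normalizing and then comparing after with before fits both sections and holds its null error. That stands, and it makes the finding an undefined variable with one misleading reading. It does not remove the finding, because Section 7.1 ties the normalization directly to estimating changes, no subtraction is mentioned, and Step 4 shows a remaining weakness in the charitable version.

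A second reply is that a task or muscle difference with no training or SCS effect is something the protocol separately expects, so detecting it is not in itself an error. That also stands. The harm comes when such a result is reported as a training or SCS effect.

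Other inferences go too far. One is that the ratio would hide or reverse a true ankle gain. That needs larger facilitation in rectus femoris, against the protocol's stated expectation for tibialis anterior; the distortion to expect runs towards the hypothesized direction. Another is that these contrasts alone address which movements are involved; Section 8's first test is itself task-specific. A third is that the protocol expects facilitation to differ between control and SCI participants. It does not say so; the group figures in Step 3 rest on an assumption.

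**Conclusion.** The point holds as an analysis variable that should be fixed before the data are seen. The plan does not say which change enters the task, joint and group comparison. The literal reading of Section 7.1 gives a test that can favour the ankle or the precision task with no training or SCS effect, and Holm-Sidak reduces this without curing it, because the quantity compared is the wrong one. The exact rates depend on facilitation ratios and SDs that the documents do not give. The direction does not depend on them, provided facilitation differs between the compared cells. For task and muscle that difference is the protocol's own expectation. Under the scaling-only reading there is no null inflation, and what remains is that equal proportional gains register as unequal changes.

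**What to change.** In Section 7.1 (Aim 1) and Section 8, define change once: the log ratio of the after-training to the before-training MEP amplitude within the same muscle, task and SCS state. For the SCS hypothesis, use the log ratio of SCS on to SCS off within the same muscle, task and time point. Use that variable in the paired test and in the task, joint and group comparisons. Keep percent of the resting baseline as a descriptive display, and state whether that baseline is recorded with or without SCS.

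The cost is wording only, since the blocks needed are already planned. The small downside is less direct comparability with reports that express results as percent of resting MEP.

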Support of limb weight may introduce a force production confound when participants have to generate torque to move their foot compared to their whole leg. If this is the case, we will perform the motor task evaluations as participants lay on their side as manual support is provided to counter the effects of gravity.

7.2 Aim 2: Determine which kinds of SCS-enabled movements are mediated by the reticulospinal tract

Using the same protocol as Aim 1, we will test whether SCS can enhance the StartReact response time and amplitude. To quantify changes in neural excitability of the reticulospinal tract, we will compare the StartReact response⁷⁰ (a shortening in response time after a startling auditory stimulus) as participants perform the motor tasks before and after BoMI training.

StartReact response: Participants will be instructed to reach the target as fast as possible after it is presented. Response time will be identified from EMG activity⁷¹ and measured when the target is presented alone (visual reaction time), when it is paired with a soft auditory stimulus (80 dB, 500 Hz, 50 ms, visual-auditory reaction time), or with a startling acoustic stimulus (120 dB, 500Hz, 50ms, visual-startle react time) presented through audio speakers (T-15, Polk Audio). To quantify changes in StartReact responses, response times under different conditions will be normalized to the baseline response.

Expected outcomes: Based on previous studies by other groups^{47,71,72}, I expect the StartReact response time to be the shortest for the startle response, where the reticulospinal tract is engaged. Furthermore, I expect that SCS will have an additional enhancement of this response, but only for tasks that require a high involvement from the reticulospinal tract. *We hypothesize that SCS will enhance the StartReact response for the range-of-motion task in proximal muscles (rectus femoris), but not for precision-control movements, or movements with distal muscles (tibialis anterior).*

8. Data Analysis and Statistical Plan

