8.4 Sample Size

We plan to include in this study a total of 100 unimpaired and 12 SCI human volunteers over the course of two years. We expect that only 90% of unimpaired and 70% of SCI subjects initially recruited will conclude the experiment. Therefore, we will need to recruit 110 unimpaired and 16 SCI volunteers in order to reach the recruitment targets.

The number of subjects has been powered from the results of previous studies using similar methods to investigate structural changes in the brain after BoMI practice^{22,73}. Although the power is adequate, it might be possible that we are unable to detect significant changes in motor capacity. If no within-subject significant changes are found in preliminary experiments, we can extend the duration of training within one session, or extend the protocol to several sessions. If no significant group changes are found, we can recruit six more SCI participants for the study (a 50% increase).

9. Management of Intercurrent Events

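### Both aims predict no SCS enhancement in some tasks and muscles, but the plan has no criterion for concluding that, and Aim 2 has no contrast between tasks or joints

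*Combined protocol and SAP*

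**What the plan says.** Aim 1 (Section 7.1 Aim 1, Expected outcomes) expects larger MEPs for precision control in the tibialis anterior. It then hypothesises that "SCS will further enhance the MEP response for these movements, but not for range-of-motion movements, or movements with proximal muscles (rectus femoris"). Aim 2 (Section 7.2 Aim 2, Expected outcomes) reverses the pattern: "SCS will enhance the StartReact response for the range-of-motion task in proximal muscles (rectus femoris), but not for precision-control movements", and the sentence goes on to exclude distal muscles as well.

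Section 8 gives the whole analysis in one paragraph. The first test is stated in these terms: "A paired sample t-test of response amplitude and latency (time from stimulation to muscle response) will be used to test the hypothesis". The hypothesis meant is a rise, after BoMI sessions under SCS, in corticospinal excitability for precision control and in reticulospinal excitability for range of motion. The second test, an additional Student's comparison of conditions, "will be performed to compare the difference between changes in corticospinal excitability induced by the type of motor task", and likewise by joint and by group. It is planned "with a Holm-Sidak adjustment for multiple comparisons". The reticulospinal response is not named for that second test.

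Section 8.4 sets the numbers: "We plan to include in this study a total of 100 unimpaired and 12 SCI human volunteers over the course of two years". It gives no alpha, sidedness, effect size or SD, and on power says only: "Although the power is adequate, it might be possible that we are unable to detect significant changes in motor capacity".

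**The concern.** Each aim asks which movements a given tract mediates. An enhancement in the predicted task and muscle answers part of that. The rest of the answer is the prediction that SCS does nothing in the other tasks and muscles. A difference test can reject equality but cannot establish it, and Section 8 supplies no margin, confidence bound or decision rule for the cells where no enhancement is predicted. The paired test is not even written for those cells.

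If a non-significant result in such a cell were reported as confirming the hypothesis, a movement could be assigned to one tract and ruled out for the other on data that cannot show it. Section 3.1 says the study is to supply the data for preparing a clinical trial, so the wording of these conclusions has a use beyond this report.

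The gap is wider in Aim 2. Aim 1 at least has a planned comparison of change between tasks and joints. Without one for StartReact, selectivity there would be read off by setting significant cells against non-significant ones.

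**Working it through.** **The plan's own figure.** The SCI sample of 12 cannot be reproduced, because Section 8.4 gives no alpha, power, effect size or SD. The number of completers can be checked: 16 recruited × 0.70 = 11.2, close to the target of 12.

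**Inputs.**
- n = 12 SCI (Section 8.4).
- n = 16 unimpaired: about that many per type of protocol (Section 7.2, Participants).
- n = 32 unimpaired: my reading, if about 16 who attend only the relevant visit and about 16 who attend all five visits both contribute (16 + 16).
- n = 18 SCI: the optional six more in Section 8.4 (12 + 6).
- Assumed, not in the documents: two-sided alpha 0.05, normal paired differences, and a true effect d of 0.5 SD of the paired difference.

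**How often a real effect gives a non-significant paired t-test.** Power = P(|T| > t(0.975, n − 1)), where T is noncentral t with n − 1 degrees of freedom and noncentrality d√n. For n = 12 and d = 0.5, the noncentrality is 0.5 × √12 = 1.73 and the critical value is 2.20. Power is 35.3%, so 64.7% are missed.

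| Setting | Missed |
|---|---|
| n = 12, d = 0.5, two-sided 0.05 | 65% |
| n = 12, d = 0.5, one-sided 0.05 | 51% |
| n = 12, d = 0.5, first Holm-Sidak step of three (alpha 0.017) | 81% |
| n = 12, d = 0.3 / 0.8 / 1.0, two-sided 0.05 | 84% / 29% / 12% |
| n = 11, d = 0.5, two-sided 0.05 | 68% |
| n = 16, d = 0.5, two-sided 0.05 | 54% |
| n = 18, d = 0.5, two-sided 0.05 | 48% |
| n = 32, d = 0.5, two-sided 0.05 | 22% |

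At n = 12, the effect detectable with 80% power is 0.89 SD.

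**Reading selectivity from significant versus non-significant cells.** Suppose SCS enhances all four task-by-muscle cells equally by 0.5 SD, so that there is no selectivity. In simulation at n = 12, given a significant target cell, at least one of the other three is non-significant in about 59% to 96% of studies, and all three are in 13% to 27%. The ranges run over between-cell correlations from 0.7 to 0. With an equal effect of 0.8 SD, at least one is non-significant in 32% to 64%.

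**Reading selectivity from a direct contrast.** In the same no-selectivity setting, a within-participant task contrast or joint contrast, unadjusted, falsely points in the predicted direction in only about 8% to 10% of studies. Aim 1 has these contrasts planned, although Section 8 does not say that they are within-participant. Aim 2 does not have them.

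**What a bound could show.** If the true effect is zero, the one-sided 95% bound excludes a margin of m SD with probability P(T > t(0.95, n − 1)), where T has noncentrality m√n. At n = 12 this is 49% for m = 0.5 and 83% for m = 0.8. At n = 32 it is 87% for m = 0.5.

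**The case against.** The strongest reply is that the plan nowhere says p > 0.05 will be taken as no effect. That is correct. A reader might infer such a rule, but the documents do not state one; what they show is that no rule is given and that no planned output other than non-significance could serve.

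The second reply is that Section 8 already tests selectivity through the task and joint comparisons. For Aim 1 this largely stands. A reader might take the 59% to 96% as the risk of falsely claiming selectivity in Aim 1, but that figure ignores these contrasts, under which the risk is about 8% to 10%. A significant contrast still shows only that one response is larger, not that the other is absent. For Aim 2 the reply fails, because the comparison is limited to corticospinal excitability.

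Third, the 65% depends on chosen inputs. The hypotheses are directional, so one-sided testing is arguable (51%). Larger effects are missed less often, and the hypotheses are not specific to the SCI group, so the unimpaired figures (54% or 22%) also apply. All of that stands, and the range should be quoted with the figure.

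Finally, this is a preliminary study that admits it may detect nothing. That lowers the stakes, but it is a reason to report an inconclusive cell as inconclusive.

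**Conclusion.** The point holds in a limited form. The predictions of no enhancement in both aims have no planned criterion, and a non-significant t-test, the only available support, is weak at n = 12: 65% of real effects are missed at 0.5 SD and two-sided 0.05, 51% one-sided, and 29% at 0.8 SD. The effect size, alpha and sidedness are my assumptions. For Aim 1 the remaining defect is one of absolute versus relative wording, since relative selectivity has a planned test. For Aim 2 the defect is larger, because selectivity would rest entirely on which cells reach significance. The documents do not support saying that the sponsor intends to equate non-significance with no effect, or that the predicted enhancements themselves cannot be tested. The change should be made, because it is cheap and alters what may be concluded.

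**What to change.** 1. In Section 7.1 Aim 1 and Section 7.2 Aim 2, restate each hypothesis as relative: a larger SCS enhancement for the predicted task and muscle than for the others.
2. In Section 8, extend the task and joint contrasts to the StartReact response, as within-participant comparisons under the same Holm-Sidak adjustment. Without this, the reworded Aim 2 hypothesis would have no planned test.
3. In Section 8, state that a non-significant test will not be taken as evidence of no effect. For each cell where no enhancement is predicted, report the SCS effect with a confidence interval or a one-sided 95% bound in the direction of enhancement (shortening, for latency). Conclude that the response is not enhanced only if the bound lies inside a margin fixed before analysis; otherwise call the result inconclusive. The sponsor must choose and justify the margin, as the documents offer no basis for one.

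Cost: changes to two hypothesis sentences and one Section 8 paragraph, plus a bound per cell from data already to be collected. No participants or procedures are added. The price is a weaker claim. With 12 SCI participants and a true effect of zero, the bound excludes 0.5 SD in only 49% of studies and 0.8 SD in 83%, so many cells will be inconclusive. The Aim 2 contrasts also enlarge the set under multiplicity adjustment.

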7.1 Procedure Schedules – Full Protocol

SCI and Controls – Complete protocol

PROCEDURE	7.2 INITIAL EVALUATION			7.3 AIM 1	7.4 AIM 2
	Visit #1 Functional Mapping	Visit #2 Range of Motion	Visit #3 Familiarization	Visit #4 TMS	Visit #5 StartReact
Kinematic recordings					
EMG recordings					
Transcutaneous SCS					
BoMI					
Motor tasks					
TMS					
StartReact					

7.2 Initial evaluation: Determine the effect of SCS on motor responses and range of motion

To determine an initial baseline for each participant, we will evaluate motor responses elicited by transcutaneous SCS in the initial evaluation phase. Participants will visit the lab for 1) a functional mapping where we measure spinal responses elicited by SCS, 2) a range of motion evaluation where we measure the range of motion on different joints with and without SCS, and 3) a familiarization phase where participants learn to control the body-machine interface using their leg movements supported by SCS.

Participants: 100 unimpaired participants and 12 participants with spinal cord injury (spinal cord injury level C4-T9) with motor impairments in the legs (complete ASIA A, or incomplete ASIA B, C, or D) and in the chronic stage of SCI (>6 months postinjury) will participate in this experiment, which will be submitted for review and approval to Washington University School of Medicine Institutional Review Board. Unimpaired participants will be recruited to perform either one of the five potential visits (Visits# 1-5) or all five visits. Approximately 16 unimpaired participants are expected to complete each type of protocol. SCI participants will be recruited for the five visits in total.

Experiments with unimpaired, control participants will be used to refine collection procedures and instruments and to prepare an improved, more refined research design that will ensure effective and high-quality data collection with SCI participants. Data collected on control subjects will also be used to establish baseline behavior for comparison of SCI participant task performance and may be used to generate generalizable knowledge.

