An increasing number of studies supports the view that SCS can restore posture, stepping, and voluntary walking in humans with SCI^{4,7,17}. The prevailing view is that by elevating the functional state of spared spinal sensory-motor networks below the lesion, residual descending pathways can transmit activity that enables and amplifies voluntary motor control¹⁵. Although epidural SCS can enable force production in paralyzed muscles⁷, whether motor improvements are mediated by the corticospinal tract or the reticulospinal remains unknown.

In a 45-min session, we will deliver non-invasive transcutaneous SCS to the lumbosacral enlargement as participants use their SCS-facilitated leg movements to control a non-invasive body-machine interface (BoMI) on a computer screen and perform game-like activities^{62,63}. To determine which kinds of SCS-enabled movements are mediated by corticospinal networks, participants will perform two motor tasks before and after training requiring different degrees of dexterity: precision control vs. maximum range of motion; using two types of movements: hip vs. ankle flexion. To quantify changes in neural excitability of the corticospinal tract, we will compare motor-evoked potentials (MEPs) elicited by transcranial magnetic stimulation of the leg motor cortex⁶⁴ as participants perform the motor tasks. We postulate that MEP responses will be enhanced for the precision-control task in distal muscles (tibialis anterior), which are thought to require a high involvement from the corticospinal tract. *Our hypothesis is that SCS will further enhance the MEP response for these movements, but not for range-of-motion movements, or movements with proximal muscles (rectus femoris).*

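### Participants with incomplete sessions are set apart and no analysis set is defined per aim, so a missed Visit 5 may keep a full Visit 4 record out of the Aim 1 test; separately, the Section 8.4 recruits fall short of their targets

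*Combined protocol and SAP*

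**What the plan says.** The rule is in the Aim 1 section, under expected outcomes, potential problems and alternative strategies. The plan foresees high attrition among severely disabled volunteers and notes that "some evaluations might be interrupted". Its response begins "To preserve uniformity of statistical power across the study" and continues "we will retain the results of participants with an incomplete number of sessions in separate data sets". It then adds: "The analysis of incomplete data sets will take explicitly into account the causes for abandoning the study".

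Section 8 names the main test: "A paired sample t-test of response amplitude and latency". It also names an adjusted t-test comparing task, joint and group (control vs SCI). It names no analysis population, overall or per aim.

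The column headings of the visit schedule place Aim 1 at Visit 4 (TMS) and Aim 2 at Visit 5 (StartReact). SCI participants are recruited for all five visits. For controls, Section 7.2 says: "Unimpaired participants will be recruited to perform either one of the five potential visits (Visits# 1-5) or all five visits". About 16 controls are expected per type of protocol.

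*Session* is not defined. The Aim 1 section uses it for the training period ("In a 45-min session"), and Section 8.4 does the same: "we can extend the duration of training within one session, or extend the protocol to several sessions". The five attendances are called visits.

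Section 8.4 expects 90% of unimpaired and 70% of SCI recruits to finish. It says that recruiting 110 and 16 will reach the targets of 100 and 12.

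**The concern.** An undefined word appears to decide who is in the main test, and nothing in Section 8 settles the matter. The reason given for the rule is uniform power across the whole study. That points to one common set of full attenders, not to a set for each aim.

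The clear problem case is someone recruited for five visits who completes Visit 4 and never has Visit 5. Under the TMS heading, Aim 1 responses are taken before and after training, with and without stimulation, and are scaled to that person's resting response before training. Such a person therefore has a full Aim 1 paired record. Setting it apart would make the Aim 1 sample depend on an attendance that Aim 1 does not need, in the scarcest group, where the plan itself expects 30% not to finish. At stake are selection of completers and, possibly, some power.

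**Working it through.** **1. The plan's own recruitment figures (Section 8.4).**
- Expected completers: 110 × 0.90 = 99.0 and 16 × 0.70 = 11.2, against targets of 100 and 12.
- Dividing by the completion rate gives 100/0.90 = 111.1, so 112, and 12/0.70 = 17.1, so 18.
- The stated figures match multiplication instead: 100 × 1.10 = 110, and 12 × 1.30 = 15.6, rounded up to 16.
- If participants complete independently, the chance of at least 100 completers from 110 is 45%, and of at least 12 from 16 is also 45%.

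**2. The text.** Two readings of *sessions* are possible. Elsewhere the word means a training period, and the sentence before the rule is about interrupted evaluations. Against that, the rule speaks of a number of sessions and is followed by the causes for abandoning the study, which fits visits better. Whether the separate data sets also enter the Section 8 tests is not stated on either reading.

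**3. How many SCI participants are affected (visit reading).** Dropouts: 16 × 0.30 = 4.8. Their timing is not given, so the Aim 1 loss is a range:
- All leave before Visit 4: 0.
- Even spread over the four gaps between visits: 4.8/4 = 1.2.
- Constant retention over four gaps: 16 × 0.70^(3/4) − 11.2 = 12.24 − 11.2 = 1.04.
- Constant retention over five steps: 16 × 0.70^(4/5) − 11.2 = 12.03 − 11.2 = 0.83.
- All leave after Visit 4: 4.8.

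If visits are taken in numerical order, Aim 2 loses nobody.

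**4. Power.** The plan gives no effect size, SD, alpha or power, so these are assumptions: SCI group only, paired t-test, two-sided 5%, standardised change dz.

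| dz | n = 11 | n = 12 | n = 16 |
|---|---|---|---|
| 0.5 | 32% | 35% | 47% |
| 0.8 | 67% | 71% | 85% |
| 1.0 | 85% | 88% | 96% |

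These figures assume that recovered pairs behave like the others. In a simulation of 200,000 runs, 11 completers with dz 0.8 were joined by 1 or 5 recovered pairs (total 12 or 16):
- Recovered pairs with 2 times the variance: 68% and 75%.
- 3 times the variance: 66% and 66%.
- 4 times the variance: 64% and 59%.
- Same variance, half the effect: 67% and 70%.

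At 3 times the variance or more, power is below the 67% obtained from the 11 completers alone.

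**5. Selection.** Suppose the leavers' mean change differs by 0.5 SD (assumed). The completer-only mean then differs from the mean of everyone with Visit 4 data by (1.2/12.4) × 0.5 = 0.05 SD under even spread, and by (4.8/16) × 0.5 = 0.15 SD at the extreme.

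**6. Control vs SCI.** Assume 16 to 32 controls with Visit 4 data (one or two protocol types of about 16). The standard error is proportional to √(1/controls + 1/SCI).
- 32 controls: 0.3495 at 11 SCI, 0.3385 at 12 (−3.2%), 0.3062 at 16 (−12.4%).
- 16 controls: 0.3917 at 11 SCI, 0.3819 at 12 (−2.5%), 0.3536 at 16 (−9.7%).

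**The case against.** The strongest reply is that the harm needs two steps the plan never takes: that sessions means visits, and that a separate data set means exclusion from the Section 8 tests. A reader might infer that incomplete participants are discarded. The documents do not support that: results are retained, and an analysis that considers the causes of leaving is promised. What stands is narrower. That analysis has no method and no link to the main tests, so membership could be settled after the data are seen.

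A reader might also infer that the rule treats SCI participants more harshly than controls who attend only Visit 4. The plan does not say how one-visit controls are classed, so unequal treatment is not established. Nor would a per-aim set make exposure equal, since such a control has not had Visits 1–3.

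It is also fair that the SCI exclusion criteria tolerate some missed appointments: exclusion 17 applies only beyond three missed without notice. The problem case therefore needs a Visit 5 that never takes place, not a postponed one.

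Finally, the effect is small and rests on assumed inputs, and the starting point of 11 comes from the separate shortfall in Section 8.4. With 12 completers, recovered participants would only add to the intended number. All of this stands and lowers the weight of the point, but the missing definition remains.

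On recruitment, Section 8.4 allows six more SCI participants. That step depends on finding no significant group change, not on attrition, so it does not repair the arithmetic.

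**Conclusion.** The point holds as a request for clarification of low priority. Established: *session* is undefined, no analysis set is given per aim, and the plan does not say whether the separated participants enter the main tests. Conditional on the visit reading: a complete Visit 4 record could be held out of Aim 1 because of later attendance. The expected cost is about one SCI participant, with bounds of 0 and 4.8 of 16 set by unknown dropout timing.

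A reader might infer a material loss of power. The documents do not support that, because the gain from recovering these pairs depends on their variance and effect, and it can vanish or reverse. The firmer argument is that a set defined by each aim's own visit does not select on a later event.

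The Section 8.4 error depends on none of this. It follows from the plan's own rates, and each group is about two recruits short of the number whose expected completers reach the target.

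**What to change.** Keep the commitment that the analysis of incomplete data takes the causes of leaving into account, and add to the Aim 1 section and Section 8:

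> Each paired comparison in the Aim 1 test includes every participant with both members of that pair recorded at Visit 4, and each in the Aim 2 test every participant with both members recorded at Visit 5, for the given task, joint and stimulation condition. Missing a later visit does not remove a participant from an earlier aim. An analysis restricted to participants who completed all their planned visits, which also removes five-visit participants who missed any of Visits 1–3, is a sensitivity analysis.

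Defining completeness pair by pair also covers evaluations that are interrupted part-way. If the sponsor means visits, use that word in place of sessions in the existing rule.

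In Section 8.4, restate the expected completers from 110 and 16 recruits as about 99 and 11, and remove the claim that these recruits reach the targets.

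The cost is wording only: no extra participants or measurements, and the paired t-test is unchanged. The downsides are that n may differ slightly between aims and between comparisons, recovered pairs may be more variable, and the stated completer figures become slightly less favourable.
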